**Remark:** The justification for the "Intercurrent Events" is that we wish to report the difference in the risk of the primary endpoint comparing the two interventions in a world where people may die of other causes within the year, thus non-cardiac death is not an intercurrent event. The estimand of interest is made clear by the population of interest being among all patients and not just those that do not die from other causes.

We recognize that by ignoring non-cardiac death, we allow for the possibility that an intervention that kills people in some unexpected way would be considered superior by our primary estimand. Thus, as outlined in Section 7.1.1, we will never report the findings of the primary analysis without also reporting a comparison of the incidence of non-cardiac death between the intervention arms.

Correspondingly, the primary clinical question of interest is:

"What are the risks of the composite endpoint among patients randomized to receive IVL for lesion preparation before implantation of newest-generation drug-eluting stents in a severely calcified coronary lesion, and how does this risk compare to using the current conventional techniques of lesion preparation, regardless of actual use of balloon lithoplasty, additional interventions performed during initial PCI or additional treatments during the one-year after procedure, or other changes in status of patients not included in the endpoint of interest?"

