## 6 Analysis Sets

- The “**Main analysis set A**” consists of all randomized participants who have a complete measure of the primary composite endpoint. This will exclude three groups of patients: patients who withdraw consent prior to 1 year and explicitly do not wish to participate in the 1-year clinical follow-up data collection, patients that are deemed to be lost to follow-up by the Clinical Endpoint Adjudication Board (see section 4.3 of protocol version 5.3), and patients who lack baseline OCT or Quantitative coronary angiography.
- The “**Sensitivity analysis set or Main analysis B**” consists of all randomized participants.
- **Secondary Safety endpoint analysis set 1, 1a, 1b, 1c:** consists of all randomized participants who have a measure of in-hospital and 1 year major adverse cardiac events for set 1, all randomized participants who have a measure of Cardiac death at or before one year after the index procedure, 1a, all randomized participants who have a measure of any myocardial infarction at or before one year after the index procedure, 1b, and all randomized participants who have a measure of stroke at or before one year after the index procedure, 1c.
- **Secondary Safety endpoint analysis set 2, 2a, 2b, 2c:** consists of all randomized participants who have a measure of in-hospital procedure events overall, 2, of periprocedural myocardial infarction, 2a, coronary dissection (beyond intended by lesion preparation), 2b, and coronary perforation/rupture, 2c. As it is very likely that all randomized participants will have measures of these events or be followed to know that the event did not occur, all of these groups may be the same as “Sensitivity analysis set or Main analysis B”

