## 7 Statistical Analyses

### 7.1 Primary Endpoint Analysis

#### 7.1.1 Main Analytical Approach

For this analysis, we will use the “Main analysis set A” detailed in Section 6. We will estimate the primary estimand, that is, the risk ratio  $\pi_1/\pi_0$ , as the empirical (i.e. observed) proportion of participants with the composite endpoint within 12 months after index PCI. An appropriate two-sided 95% confidence interval and matching p-value for the null hypothesis:  $H_0 : \pi_1/\pi_0 = 1$  will be computed.

We will use the function `uncondExact2x2` of the R package `exact2x2`; see [2] for the mathematical details and Appendix 9.2 for the specific R code that we will use. If the p-value is  $\leq 0.05$  and the risk ratio is  $< 1$  for the composite primary endpoint then we will consider this evidence of the superiority of balloon lithoplasty preparation of lesions in comparison to current conventional techniques to reduce the risk of the composite endpoint. If the p-value is  $\leq 0.05$  and the risk ratio is  $> 1$ , we will consider this evidence of harm of balloon lithoplasty preparation of lesions in comparison to current conventional techniques, i.e. it increases the risk of the composite endpoint.

Using dataset “Main analysis set B” detailed in Section 6, we will, in addition, estimate the difference in risk  $\pi_1 - \pi_0$  of all mortality that is not cardiac death within at least 12 months; the competing risk of the composite endpoint. An appropriate exact two-sided 95% confidence interval for the parameter  $\pi_1 - \pi_0$  will be computed. This will be reported regardless of the result of the above analysis. We will again use the function `uncondExact2x2` of the R package `exact2x2`; see

[2] for the mathematical details and Appendix 9.2 for the specific R code that we will use. The primary composite endpoint results will never be presented without the results for all other causes of mortality unless there are no other deaths in the full trial.

In addition, regardless of the results, we will report the estimates of the arm-specific risk of the composite endpoint and the risk of mortality that is not cardiac death within one year (i.e. the empirical proportions) together with exact binomial two-sided 95% confidence intervals (computed using the `binom.test()` function of R).

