### 7.3.1 Secondary Safety Sensitivity Analyses

Just as in the main analysis, if there are missing values in any of the safety datasets, 1, 1a, 1b, 1c, 2, 2a, 2b, or 2c, we will report the best/worst case bounds Gabriel et al. [5]. There will be no additional sensitivity analysis for the secondary efficacy endpoints.

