## 8 Sample Size Determination and Power Calculation

In the protocol, it was stated that to reach 80% power to detect a true difference of 15%, with 25% in the standard of care group and 10% events in the IVL group for a two-sided test with alpha of 0.05, 194 patients total, 97 per arm, are needed when randomized 1:1. However, it was planned to enroll 200 patients to allow for a low level of loss to follow-up.

Instead, when using the intended exact method, we find that 194, 97 per arm, only provides 78% power for the hypothesized true difference in risks. Using the intended enrollment of 100 per arm, we reach the desired 80% power. These power calculations were carried out using the Power2x2 function, as outlined below.

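### The compulsory non-cardiac mortality comparison counts patients of unknown vital status as non-events, has no best/worst-case bounds, and states its time window inconsistently

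*SAP*

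**What the plan says.** The Remark in SAP section 3.1.1 accepts that the primary estimand ignores non-cardiac death, and so could favour an intervention that kills by an unexpected route. As the safeguard, it promises never to report the primary findings "without also reporting a comparison of the incidence of non-cardiac death between the intervention arms".

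Section 7.1.1 carries this out. On Main analysis set B it estimates the risk difference "of all mortality that is not cardiac death within at least 12 months; the competing risk of the composite endpoint", with an exact 95% confidence interval. Arm-specific risks are reported as empirical proportions with exact binomial intervals, and here the window is one year.

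Section 6 says that Set B "consists of all randomized participants". It sets no condition that the outcome be known. Set A, used for the primary analysis, leaves out three groups that Set B keeps: "patients who withdraw consent prior to 1 year and explicitly do not wish to participate in the 1-year clinical follow-up data collection", patients judged lost to follow-up, and patients without baseline OCT or quantitative angiography.

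Best/worst-case bounds appear in two places. Section 7.1.2 applies them to missing composite outcomes. Section 7.3.1 applies them "if there are missing values in any of the safety datasets, 1, 1a, 1b, 1c, 2, 2a, 2b, or 2c". Set 1a is cardiac death. Non-cardiac death is in neither list.

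**The concern.** A proportion over all randomised patients needs a status for each of them. Two of the three groups that Set B adds to Set A, the withdrawn and the lost, are those whose vital status may be unknown at 12 months. The SAP gives no rule for them in this comparison. Under the stated denominator they become non-events.

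This differs from the rest of the plan. Section 7.1.2 recognises that drop-out related to outcome and differing by arm can make an analysis anti-conservative, and it plans bounds for that reason. Cardiac death (1a) has an analysis set limited to measured patients, plus bounds. Non-cardiac death, the SAP's own protection against calling a harmful intervention superior, has neither. If losses differed by arm, a true difference could be masked or a false one suggested, and no planned analysis would show how far the missing status could move the estimate.

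The window is a second, smaller fault. A period of at least 12 months has no upper end, so it is unclear whether a death after day 365 counts. Section 7.4.2 expects the 12-month visit to fall slightly early or late.

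**Working it through.** **1. The plan's own figures.** Section 8 assumes event rates "with 25% in the standard of care group and 10% events in the IVL group" for a "two-sided test with alpha of 0.05", and says that 97 per arm "only provides 78% power for the hypothesized true difference in risks" and that 100 per arm reaches 80%. Full enumeration of the unconditional exact test (tables ordered by the one-sided Fisher mid-p, maximised over the common rate, two-sided p taken as twice the one-sided p) gives 78.2% at 97 per arm and 80.3% at 100. The stated power reproduces, so sample size is not at issue. Section 8 is used below only for scale: 200 − 194 = 6 patients allowed for loss, or 3 per arm.

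**2. How unknown status enters.** For each arm let n be the number randomised, d the known non-cardiac deaths and m the patients of unknown 12-month status (subscript 1 for IVL, 0 for control).

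- As planned on Set B: RD = d1/n1 − d0/n0. This does not depend on m, so every unknown is scored as a non-event.
- Known status only: d1/(n1 − m1) − d0/(n0 − m0).
- Best/worst-case bounds: lower = d1/n1 − (d0 + m0)/n0; upper = (d1 + m1)/n1 − d0/n0. The width is m1/n1 + m0/n0, whatever the number of deaths.

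**3. Illustration.** The SAP gives neither expected non-cardiac deaths nor expected unknowns. All counts here are assumptions, with 100 per arm.

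| Deaths IVL / control | Unknown IVL / control | RD on Set B (points) | RD, known status | Bounds (points) | Width |
|---|---|---|---|---|---|
| 2 / 2 | 3 / 3 | 0.0 | 0.0 | −3 to +3 | 6 |
| 2 / 2 | 5 / 1 | 0.0 | +0.09 | −1 to +5 | 6 |
| 2 / 3 | 3 / 3 | −1.0 | −1.03 | −4 to +2 | 6 |
| 2 / 3 | 5 / 1 | −1.0 | −0.93 | −2 to +4 | 6 |
| 2 / 3 | 5 / 5 | −1.0 | −1.05 | −6 to +4 | 10 |
| 2 / 3 | 10 / 10 | −1.0 | −1.11 | −11 to +9 | 20 |

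First row in full: lower = 2/100 − (2 + 3)/100 = −0.03; upper = (2 + 3)/100 − 2/100 = +0.03. Second row, known status: 2/95 − 2/99 = 0.02105 − 0.02020 = +0.0009.

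**4. Against the planned interval.** Asymptotic score intervals, standing in for the SAP's exact ones, are about −5.2 to +5.2 points for 2/100 v 2/100 and about −6.5 to +4.3 for 2/100 v 3/100. The bounds in the rows with 6 unknowns in total, and in the 5 / 5 row, lie inside these. Those in the 10 / 10 row do not. In the worst case there, 12/100 v 3/100, the interval is about +1.9 to +17.1 and excludes zero. The interval and the bounds measure different things: the first is sampling error with every status taken as known, the second is what unknown status could do to the estimate itself.

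**5. The window.** Section 7.1.1 uses a period of at least 12 months for the risk difference and one year for the arm-specific risks of the same event. Read literally, the two could count different deaths, and the difference need not equal the difference of the reported proportions.

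**The case against.** **The SAP never says that unknowns are counted as alive.** True. A reader might infer it from the code in section 9.3, which takes only events and patient numbers. That does not follow: the code in 9.2 has the same form and is run on Set A, where unknowns are already excluded. The code takes whatever n is supplied. What fixes the denominator is section 7.1.1 naming Set B, the Set B definition, and the use of empirical proportions. Dropping unknowns would contradict that definition. The exact consequence is that they count as not having died of a non-cardiac cause.

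**There may be no unknowns.** This stands. Vital status may be obtained for everyone, and the protocol, not available here, may describe how. Patients who lack only OCT or angiography need not have unknown vital status. The 6-patient allowance is for loss to follow-up in the primary analysis, not for unknown vital status.

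**Different sets for the two results.** A reader might see the use of Set A for the composite and Set B for mortality as a defect. It is not. Restricting mortality to Set A could discard known deaths, and section 7.3 explains that safety analyses should use all available data.

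**Loss would be visible.** A reader might infer that nothing planned would reveal differential loss. The flow diagram (7.4.6) and the by-arm summary of non-completers (7.4.4) would show it, and the bounds for cardiac death would hint at its effect. The cumulative incidence display in 7.2 is also relevant, though no estimate from it is specified. None of these bounds the non-cardiac difference.

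**The confidence interval already covers the illustrated range.** This holds for the smaller examples, so the reader is not left with a bare 0.0. But the interval does not respond to the number of unknowns.

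**Conclusion.** The point holds in a limited form. By its stated denominator, the compulsory non-cardiac mortality comparison scores patients of unknown vital status as non-events, and it is left out of bounds that the plan already applies to the composite and to cardiac death. The size depends on a number that the SAP does not give. With about 3 unknown per arm the point estimate is practically unchanged (−1.00 v −1.03 points in the example), and what is lost is a statement of uncertainty 6 points wide. With 10 unknown per arm the width is 20 points, and the worst case could change the reading. If all vital statuses are known, this part disappears. The SAP does not support a claim that the comparison is seriously biased or that it conceals harm.

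The inconsistent window stands whatever the number of unknowns. Both are worth correcting, because the SAP relies on this comparison to qualify its primary conclusion.

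**What to change.** In sections 7.1.1 and 9.3:

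- Keep all randomised patients as the target population. Do not restrict to Set A.
- Compute the estimate in patients with known 12-month vital status, or by cumulative incidence with censoring at the date last known alive.
- Report the number with unknown vital status by arm, next to the estimate.
- If any are unknown, apply the best/worst-case bounds of 7.1.2 to non-cardiac death over Set B.
- Define the window as within 12 months after index PCI, and use it for both the risk difference and the arm-specific risks.

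The cost is a few lines of SAP text, one more run of bounds already planned, and a somewhat wider stated uncertainty. The primary test and sample size are unaffected.

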Note that the above statistical analyses will ignore that the randomization was stratified by site. This is usually not recommended, as this usually leads to a decrease in power as stratification variables are precision variables [3, 7]. However, our context is very specific, as we expect for there to be a low number of composite endpoint events, at least in the IVL arm. This has two important consequences. First, the loss of power is expected to be negligible. Second, ensuring proper type-I error control using a “covariate-adjusted” alternative approach is difficult using standard software. Additionally, the impact of not adjusting will be investigated as part of the Sensitivity Analyses.

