As part of the sensitivity analysis, we will adjust individually and collectively, if possible, for several variables known to be strongly predictive of the composite outcome but not used as stratifying variables for randomization. Thus, if by chance they are imbalanced in randomization, adjustment for them may reduce the effect of interest. In each regression, we will also adjust for site, with an indicator for each site that has at least three events and combining sites that are geographically close as needed when less than three events have occurred within a site. This will provide the correct standard error estimates since the randomization was stratified by site. For this reason, the results may be more significant or significant when the primary analysis is not, regardless of the results of the sensitivity analysis adjusting for site; this analysis will not replace the primary analysis in the publication as it does not strongly control the type I error rate. The additional variables include:

- Presentation (acute vs. chronic)
- Prior revascularization
- Diabetes mellitus
- LAD vs non-LAD

Logistic regression, including both main effects and interactions with treatment assignment, will be considered whenever possible; we will obtain marginal risk ratios via standardization (g-computation). Example code is provided in the code section 9.2. If this is not possible, i.e. the method will not converge due to the lack of events, we will run a main effect only model.

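### Does the plan need a separate site-only analysis, and a new fallback rule, to keep its promise to examine the effect of ignoring site in the primary test?

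*SAP*

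**What the plan says.** SAP section 7.1.1 states that the primary test ignores the stratification by site. It concedes that this is not usual practice, and gives two reasons: a negligible expected loss of power, and the difficulty of controlling type I error with an adjusted method when events are few. It adds that "the impact of not adjusting will be investigated as part of the Sensitivity Analyses".

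Section 7.1.2 describes the regressions: "we will adjust individually and collectively, if possible, for several variables known to be strongly predictive of the composite outcome". The four variables are presentation, prior revascularisation, diabetes and LAD location. On site it says: "In each regression, we will also adjust for site, with an indicator for each site that has at least three events"; sparser sites are combined with neighbours. It then says "For this reason, the results may be more significant or significant when the primary analysis is not", adds "regardless of the results of the sensitivity analysis adjusting for site", and ends that sentence with "this analysis will not replace the primary analysis in the publication as it does not strongly control the type I error rate".

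The model is logistic with treatment interactions where feasible, standardised to a marginal risk ratio. The fallback applies if "the method will not converge due to the lack of events, we will run a main effect only model". On software: "Example code is provided in the code section 9.2".

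**The concern.** Three things look wrong.

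- **Site is not isolated.** The paragraph in 7.1.1 that makes the promise concerns site only, and 7.1.2 speaks of a site-adjusted analysis as though it were defined. Yet every regression listed there changes three things against the primary test: exact to model-based inference, site, and at least one covariate. A difference could be credited to the stratification when the covariates produced it.
- **The fallback may not fire.** With separation (a cell with no events, or only events), logistic software usually reports convergence although a coefficient is drifting to infinity. A rule that waits for non-convergence could then leave an unstable model in place.
- **The code is missing.** Section 9.2 holds the exact test, 9.1 the power calculation and 9.3 the interval for other mortality. None holds g-computation code, and no interval method for the marginal risk ratio is stated.

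At stake would be the evidence for an admitted departure from usual practice, and the reliability of the supportive risk ratios.

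**Working it through.** **1. The plan's own figures.** Inputs from SAP section 8: risks 25% and 10%, two-sided alpha 0.05, 97 or 100 per arm. Enumerating all 2x2 tables for the unconditional exact test (mid-p Fisher ordering, p maximised over the nuisance risk) gives power of 78.2% at 97 and 80.3% at 100 per arm. The SAP states 78% and 80%. The sample size is not in question.

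**2. Why site alone can do little.** In a logistic model with treatment and site as main effects, the score equations make the mean fitted risk in each arm equal the observed proportion. If each site is split exactly 1:1, the site mix is the same in both arms, so standardising over all patients returns those same proportions. The site-adjusted risk ratio then equals the crude one. Only incomplete blocks can move it.

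**3. Size of the shift.** The SAP gives no number of sites, site variation or covariate effects, so these are assumed: 200 patients; 3, 5, 10 or 20 sites; site SD 0.5 on the logit scale; four covariates with prevalence 0.35 to 0.50 and odds ratios 1.0 to 2.0; permuted blocks of 4; sites with under three events merged; main-effects models.

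| Model | SD of shift in log risk ratio from crude | Significance differs from exact test |
|---|---|---|
| Site alone | 0.000 (exact balance); 0.006 to 0.024 (incomplete blocks) | 0.4% to 1.8% |
| Site + one covariate | 0.024 to 0.053 | 1.8% to 3.8% |
| Site + four covariates | 0.050 to 0.102 | 3.5% to 7.5% |

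For scale, the standard error of the crude log risk ratio at 100 per arm is sqrt(0.90/10 + 0.75/25) = sqrt(0.12) = 0.346. The largest site-alone SD is 0.024/0.346 = 7% of that. With site SD from 0 to 1.0, site alone changes power by -0.2 to +1.7 points, multiplies the standard error by 0.973 to 0.995, and changes significance in 0.4% to 3.0% of trials.

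A second simulation (2, 4, 8 or 12 equal sites; site SD 0, 0.5 or 1; covariate log odds ratios 0.4; 600 trials per setting) gave mean absolute shifts of 0.000 to 0.016 for site alone and 0.048 to 0.056 for site plus four covariates.

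**4. The fallback.** The first simulation found separation in:

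- at most 0.5% of main-effects fits;
- 1% to 13% of fits if only the covariates are interacted with treatment;
- if site is interacted too, 18% to 27% (3 sites), 41% to 50% (5), 69% to 81% (10) and 88% to 93% (20).

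All 2,571 + 27,529 = 30,100 separated fits were flagged as converged; 372 + 2,084 = 2,456 (8%) gave a warning. So the trigger does miss separation.

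The reported quantity survives, because standardisation averages fitted risks, not coefficients. Take five sites with 20 patients per arm each, one site having 0 IVL events and 5 conventional events. The fit stops after 16 iterations with a treatment coefficient of -16.5. The fitted IVL odds in that site are (5/15) x exp(-16.5), about 2 in 100 million: in effect the observed 0 of 20.

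With site interacted, the median risk ratio was 0.39 to 0.41 (true 0.40) and coverage 93% to 96%. Rejection under the null (17.5% risk in both arms) was 4.3% to 6.3%, against 4.8% to 5.2% for main effects with four covariates and 4.1% to 4.8% for the exact test (Monte Carlo SE about 0.3 points).

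**5. The code reference.** Section 7.1.1 also cites 9.2 for the risk-difference code, which stands in 9.3. The cross-references to section 9 are loose in general. The method itself, logistic regression standardised to a marginal risk ratio, is named in the text.

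**The case for a change.** The case for a change is that the SAP departs from what it calls usual practice and offers a check in support, yet lists no model that isolates site. It also credits extra significance to the stratification. In the simulations, where the four-covariate model was significant and the exact test was not, the site-only model was also significant in just 4% to 40% of cases. A few sentences before unblinding would close the gap.

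The textual facts stand: no treatment-plus-site model of the primary endpoint is written out, the trigger can miss separation, and the code is absent. The attribution point stands in part, though it depends on the assumed covariate effects: with 20 sites and covariates unrelated to outcome, the contrast shrinks to 0.022 for site against 0.033 to 0.034 for site plus one covariate.

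What does not follow is that the plan would report something wrong. The promise does not specify site alone, and site is in every regression with a rule for sparse sites. The high separation rates need a site-by-treatment interaction that the SAP does not state; its interaction sentence follows directly after the list of four covariates.

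The obvious repairs are no clear gain either. Entering site as a main effect only leaves the 1% to 13% separation from covariate interactions without a trigger. A trigger on empty site-by-arm cells ignores covariate cells and would fire often: with about 25 of 35 events expected in the conventional arm, a three-event site has no IVL event with probability about (25/35)^3 = 0.36.

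**Conclusion.** No change follows. The site-only model is a detail that the SAP already presumes. Analysts can add it from the model in 7.1.2 by dropping the covariates, and under the assumed settings it would move the log risk ratio by an SD of at most 0.024. That supports the plan's expectation of a negligible power loss. The fallback trigger is loosely worded, but no material error in the marginal risk ratio was found: even the highest null rejection, 6.3%, occurs in models that the SAP bars from replacing the primary analysis and describes as lacking strong type I error control. The reference to 9.2 is clerical, and a standard interval for a standardised risk ratio (the delta method was used here) fills the gap.

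The sizes rest on assumed site numbers, site variation and covariate effects, none of which the SAP gives. Two independent sets of assumptions agree on the order of magnitude. The primary test, its power and its conclusion are untouched.
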